15.2 Site Investigators Assessment

Once participants are randomised into the trial and the local PI confirms eligibility, the participants will be under the care of staff at the trial co-ordinating centre (HAL, QMUL). The local PI at HAL will be responsible for their care (or in his/her absence an authorised medic within the research team) and assessment of any event for:

Seriousness

Assessing whether the event is serious according to the definitions given in section 15.1.

Causality

Assessing the causality of all serious adverse events/reactions in relation to the trial treatment according to the definition given. If the SAE is assessed as having a reasonable causal relationship, then it is defined as a SAR.

Expectedness

Assessing the expectedness of all SARs according to the definition given. If the SAR is unexpected, then it is a SUSAR.

Severity

Assessing the severity of the event according to the following terms and assessments. The intensity of an event should not be confused with the term "serious" which is a regulatory definition based on patient/event outcome criteria.

- o Mild: Some discomfort noted but without disruption of daily life
- Moderate: Discomfort enough to affect/reduce normal activity
- Severe: Complete inability to perform daily activities and lead a normal life

15.3Reference Safety information

The SmPC for the Nicorette Invisi 15mg Patch (section 4.8, version: 25 May 2016) will be used for assessing whether an adverse reaction is expected.

15.4 Recording of Adverse Events or Reactions

The following are considered expected AEs/ARs:

Symptoms which are potentially caused by NRT/EC use and are listed as known events/reactions in the SmPC for patch, which include: rash/local skin irritation; nausea/vomiting; headaches; dizziness. Known reactions to EC include dislike of taste, cough and throat/mouth irritation.

All AEs and ARs will be recorded in the e-CRF and the participant followed up by the research team to resolution as appropriate. AE's will begin to be recorded from receipt of the study product by the participant until the end of the follow-up period.

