10.3.2 Secondary Endpoints

Changes in smoke intake and in nicotine intake indexed by salivary anabasine and salivary cotinine levels, assessed for participants still using NRT or EC at end of pregnancy and for 'dual users' or those who have reduced their smoking by 50% or more; 7-day point-prevalence abstinence self-reported at 4 weeks, end of pregnancy and at 3 months post-partum; self-reported prolonged abstinence at end of pregnancy and 3 months post-partum; use of NRT and EC throughout pregnancy; proportion of participants reporting adverse events and serious adverse events in each group; proportion of participants in each group reporting adverse events and serious adverse events for themselves or their infant at 3 months post-partum; birth and maternal outcomes.

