10.5 Objectives and End Points Summary

Primary Objective	Primary Endpoint	Outcome Measures
Efficacy of EC compared to	Abstinence rates in each	Prolonged abstinence at end of
NRT	group at end of	pregnancy from 2 weeks post-
	pregnancy	TQD defined as per Russell
		Standard abstinence criteria,
		biochemically validated
Secondary Objectives	Secondary Endpoints	Outcome Measures
Effects on Smoke and	Change in smoke and	Salivary cotinine and anabasine
Nicotine intake from EC and	nicotine intake from	
NRT users; 'dual users'; and	baseline to end of	
reducers (50% or more)	pregnancy	
Efficacy of EC compared to	Abstinence at 4 weeks	Self-reported point prevalence
NRT	post-TQD, end of	abstinence (not a puff over the
	pregnancy, and 3-	previous week) at 4 weeks post-
	months post-partum.	TQD, at end of pregnancy and at 3
		months post-partum; self-
		reported prolonged abstinence at
		end of pregnancy and at 3-
		months post-partum
Treatment adherence	Use of EC and NRT	Self-reported EC and NRT use
		(number of days used; amount
		and products used; product
		changes)
Safety of EC compared to	Adverse events	Self-reported adverse events and
NRT	throughout the	SAE's
	intervention period and	
	at 3 months post-	SAE's identified at 3-months post-
	partum (for both	partum follow-up calls.
	mother and infant).	
	Birth and maternal	Birth and maternal outcomes:
	outcomes	Birth weight; gestational age; C-
		section delivery; still
		birth/miscarriage/neonatal or
		post-neonatal death; maternal
		death; neonatal intensive care
		admission

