Electronic cigarette: The study will use a TPD-approved refillable EC (Innokin Endura T18; TPD product ID: 00132-16-00001) with a tobacco flavoured e-liquid with nicotine content of 18mg (fruit flavour e-liquid will be offered in cases where participants dislike the tobacco flavour). EC are a consumer product and this is an open label trial and so there are no special labelling or packaging requirements. Each person will be dispensed the starter kit with an initial supply of e-liquid and offered further supplies over the phone for up to 8 weeks. Supplies will be sent via recorded delivery.

Dose modifications: Participants who find their products too strong will be offered 10mg nicotine patches or 11mg eliquid.

Weekly phone calls:

Participants will receive guidance on using their allocated product and support in preparation for the Target Quit Date (TQD), on the TQD, and weekly for four weeks thereafter (6 calls in total). The schedule and content of calls will follow the established protocols of pro-active telephone counselling for smokers (e.g. [44]). This support addresses issues such as planning for the quit day and how to deal with difficult situations, such as others smoking around the quitter. We will also collect smoking status and monitor use of EC and NRT and any other stop smoking medications, and adverse events. Study staff will also complete the study questionnaires with the participants.

End of pregnancy phone call (35 week gestation to ten weeks post-partum)

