15.1 General Definitions

Term	Definition
Adverse Event (AE)	Any untoward medical occurrence in a participant to whom a medicinal product has been administered, including occurrences which are not necessarily caused by or related to that product.
Adverse Reaction (AR)	An untoward and unintended response in a participant to an investigational medicinal product which is related to any dose administered to that participant. The phrase "response to an investigational medicinal product" means that a causal relationship between a trial medication and an AE is at least a reasonable possibility, i.e. the relationship cannot be ruled out. All cases judged by either the reporting medically qualified professional or the Sponsor as having a reasonable suspected causal relationship to the trial medication qualify as adverse reactions.
Serious Adverse Event (SAE)	 A serious adverse event is any untoward medical occurrence that: Results in death. Is life-threatening. Requires inpatient hospitalisation or prolongation of existing hospitalisation Results in persistent or significant disability/incapacity. Consists of a congenital anomaly or birth defect. Other 'important medical events' may also be considered serious if they jeopardise the participant or require an intervention to prevent one of the above consequences. NOTE: See 17.6 for events related to underlying pregnancy that will not be reported
Serious Adverse Reaction (SAR)	An adverse event that is both serious and, in the opinion of the reporting Investigator, believed with reasonable probability to be due to one of the trial treatments, based on the information provided.
Suspected Unexpected Serious Adverse Reaction (SUSAR)	A serious adverse reaction, the nature and severity of which is not consistent with the information about the medicinal product in question set out in the Reference Safety Information (RSI): In the case of a product with a marketing authorisation, in the summary of product characteristics (SmPC) for that product. In the case of any other investigational medicinal product, in the investigator's brochure (IB) relating to the trial in question.

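### Section 15.4 lists dislike of taste as an expected adverse event or reaction for e-cigarettes, which conflicts with the definition in 15.1 and lets flavour preference into the by-arm AE proportion

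*Protocol*

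**What the plan says.** Section 15.4 opens its list with "The following are considered expected AEs/ARs". The symptoms taken from the patch product information follow, "which include: rash/local skin irritation; nausea/vomiting; headaches; dizziness", and then the EC items: "Known reactions to EC include dislike of taste, cough and throat/mouth irritation". The recording rule comes next: "All AEs and ARs will be recorded in the e-CRF".

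Section 15.1 defines an adverse event as "Any untoward medical occurrence in a participant to whom a medicinal product has been administered", whether or not the product caused it. It defines an adverse reaction as a response to an investigational medicinal product. Section 14.1 says that the EC is not one.

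Among the secondary endpoints in section 10.3.2 is the "proportion of participants reporting adverse events and serious adverse events in each group". Section 10.5 gives the measure as self-report.

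Section 12.8.1 deals with taste as part of product supply: "fruit flavour e-liquid will be offered in cases where participants dislike the tobacco flavour".

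**The concern.** An item must be an AE or AR before it can be an expected one. By placing dislike of taste in that list and then ordering all AEs and ARs to be recorded, 15.4 tells staff to enter a flavour complaint as an event. Section 15.1 points the other way, because not liking a flavour is a preference and not plainly a medical occurrence.

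The ambiguity falls unevenly on the two groups. E-liquid taste can be disliked almost only by women given an EC. A woman who simply finds the patch unpleasant has no listed item, and her complaint would not meet 15.1 either. The trial is open label and AEs are self-reported, so nothing later in the process evens this out. At stake is the interpretation of one secondary safety comparison, the overall AE proportion by group, if preference and symptoms are pooled in it.

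**Working it through.** **Step 1: the provisions side by side.**

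| Section | Effect on a taste-only report |
|---|---|
| 15.4, list | Classed as an expected AE/AR for EC |
| 15.4, recording rule | To be entered in the e-CRF |
| 15.1, AE | Must be an untoward medical occurrence; not plainly met |
| 15.1, AR, with 14.1 | Must be a response to an IMP; the EC is not an IMP |
| 10.3.2 | If recorded as an AE, the woman counts in the by-group proportion |

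Sections 15.4 and 15.1 give different answers to the same question, and 10.3.2 depends on which is followed.

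**Step 2: group size.** The illustration uses 570 per group from section 17.1. That figure reproduces. For 8% versus 14%, two-sided alpha 0.05, 90% power, pooled variance and no continuity correction:

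n = [1.960·√(2·0.11·0.89) + 1.282·√(0.08·0.92 + 0.14·0.86)]² / 0.06² = 570 per group after rounding up, 1,140 in total.

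The stated 80% power for 8% versus 13.1% also reproduces (0.801). The point itself does not depend on the sample size.

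**Step 3: formula.** Let p be the proportion with any AE apart from taste, t the proportion of EC women reporting taste dislike, and c the share of those women who also report another AE. Counting taste adds t(1 − c) to the EC proportion. This is never negative. If taste dislike is independent of other AEs, c = p and the addition is t(1 − p).

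**Step 4: illustration.** The protocol gives no AE or taste rates, so these are assumptions: p = 20–60%, equal in both groups; t = 2–10%; independence; every taste dislike recorded as an AE; no patch-only reactions. The last column is the chance of a significant EC excess at 570 per group when the proportions without taste are equal.

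| p | t | EC proportion with taste counted | Added (points) | Chance of significant EC excess |
|---|---|---|---|---|
| 20% | 2% | 21.6% | 1.6 | 0.10 |
| 20% | 5% | 24.0% | 4.0 | 0.37 |
| 20% | 10% | 28.0% | 8.0 | 0.89 |
| 40% | 2% | 41.2% | 1.2 | 0.06 |
| 40% | 5% | 43.0% | 3.0 | 0.18 |
| 40% | 10% | 46.0% | 6.0 | 0.53 |
| 60% | 2% | 60.8% | 0.8 | 0.05 |
| 60% | 5% | 62.0% | 2.0 | 0.10 |
| 60% | 10% | 64.0% | 4.0 | 0.29 |

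Example: 0.20 + 0.10 × (1 − 0.20) = 0.28.

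**Step 5: overlap.** If half of the women who dislike the taste also report, say, cough or throat irritation (c = 0.5), then with t = 10% the addition is 0.10 × 0.5 = 5 points, against 8 under independence at p = 20%.

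**Step 6: patch-only reactions.** Section 15.4 also lists local skin irritation. Suppose 10% of patch women have one, independently of other AEs. Over the same grid the EC-minus-patch difference with taste counted then runs from −6.4 to 0 points. At p = 20% and t = 10% both groups stand at 28%. Without the taste item they would be 20% (EC) and 28% (patch). The net difference is zero in that case only because a preference in one group has hidden a symptom excess in the other.

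**The case against.** The best defence is that 15.4 lists what is expected and is not a counting rule. All AEs and ARs in both groups are to be recorded, listed or not, and the patch list is open-ended. So a reader who infers that patch events count only if they are in the product information goes too far: nothing sets different counting rules by group. That stands. It does not remove the conflict, because the list still names taste dislike as an AE/AR.

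A reader might also infer that patches have no counterpart at all, or that taste complaints cannot arise in the control group. Neither is supported. Patch-site skin irritation is listed, though it is a symptom and not a preference. The flowchart in section 9.0 asks control women about EC use at the end of pregnancy, so some may have used one.

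The strongest inference would be that the AE comparison is biased against EC, perhaps nearly certain to be falsely significant. With 20% taste dislike and 30–50% underlying AEs, the formula does give a 93–99.8% chance. Every input to that figure is assumed, including independence and complete recording of taste dislike as an AE. The net difference also depends on patch-only reactions. The documents establish the direction of the effect on the EC proportion, but not its size or a net bias.

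There are two further fair points. Offering another flavour does not prove that taste is mere preference: section 14.14 supplies a lower-strength patch for nausea, which is plainly an AE. And an unpleasant taste could be read into the mild grade in 15.2, so recording it for completeness is defensible. Both leave the status of taste dislike unclear, which is the point. Finally, the SAP is not to hand and may tabulate events by type. That would make the item visible, but would not reconcile 15.4 with 15.1.

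**Conclusion.** This is a minor definitional inconsistency that is worth correcting. Section 15.4 classes dislike of taste as an expected AE/AR and has it recorded; 15.1 would not plainly admit it; and no patch preference item matches it. Taste-only reports can therefore enter the AE proportion in 10.3.2, and they can only move the EC figure upward.

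The amount cannot be obtained from the protocol. Under the assumptions in the illustration it is 0.8 to 8.0 percentage points, and smaller if women who dislike the taste also report other AEs. At the low end it would be undetectable. At the high end it could produce or mask a difference. SAEs, birth and maternal outcomes, the primary endpoint and the sample size are untouched, so the safety objective as a whole is not undermined.

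**What to change.** State in 15.4 that dislike of taste alone is not an adverse event. Record it on the existing product-use questions as acceptability, with an equivalent item on dislike of the patch. Keep genuine symptoms, including cough, throat or mouth irritation and skin reactions, as AEs in whichever group they occur.

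Compute the AE proportion in 10.3.2 on events that meet the medical-occurrence criterion of 15.1. Apply that criterion identically in both groups, and say explicitly that it covers EC users, since 15.1 is worded around medicinal products. Tabulate taste-only reports separately by group so that no information is lost.

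The cost is one line in 15.4, one coding rule for the e-CRF and the SAP, and one acceptability item on calls already planned. The only downside is that the taste complaint moves from the AE table to an acceptability table.

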15.5 Notification of AEs of special interest

There are no AESIs identified for this study.

15.6 Serious Adverse Events that do not require expedited reporting

The following will be considered **expected serious adverse events (SAEs) and will not be reported in an expedited manner** (see section 15.7) but will be recorded.

Events requiring hospital admission (overnight stay) which are related to the underlying pregnancy, these include: recognised pregnancy or postnatal complications, including pre-term delivery, low birth weight, birth injury, infection, thrombosis, haemorrhage, hypertensive disease, instrumental delivery, caesarean section, and antenatal admissions for pregnancy related diseases such as false labour, infection, thrombosis, haemorrhage, hypertensive disease, suspected or confirmed foetal compromise, vaginal bleeding foetal congenital abnormalities, and infant hospital admissions; and incidental hospital admissions for minor, gastrointestinal diseases, respiratory, cardiac, renal skin, psychiatric and neurological problems.

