15.7 Notification and Reporting of Serious Adverse Events & SUSARs

The following will be considered Serious Adverse Events (SAEs) which will require reporting: Baby: foetal death, still birth, neonatal and post-neonatal death; Maternal: maternal death. Other events requiring hospital admission (overnight stay) apart from those related to the underlying pregnancy or a pregnancy related condition. SAEs will begin to be recorded from receipt of the study product by the participant. Unresolved SAEs will be followed up until the end of the study at three months post-partum if the participant is still using the study product.

All Serious Adverse Event (SAEs) will be reported to Barts CTU, acting on behalf of the sponsor, within 24 hours of the PI or research team becoming aware of the event. SARs must also be reported to Barts CTU, acting on behalf of the sponsor, within 24 hours of the PI or research team becoming aware of the event. The Barts CTU will email the de-personalized SAE to the sponsor within 1 working day of receipt.

Day zero for reporting to the MHRA is the day that the Barts CTU is notified of a medically assessed SUSAR. SAEs should also be recorded in the patient notes and the e-CRF.

The initial report must be made by completing an SAE e-CRF accessible via the web application. In addition the SAE e-CRF must be signed electronically within the web application by the PI or delegate. If for any reason the web application cannot be accessed, a paper SAE CRF should be completed and faxed or emailed. Staff should ensure that any patient identifiable information is not contained in any paper CRFs or documents when transferring forms. Any such information should be blacked out and information not visible.

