15.8 Sponsor Medical Assessment

Sponsor has delegated the responsibility for oversight of IMP safety profile and medical assessment of SAEs and SUSARs to the CI. The CI (or CI's delegate in his absence) must review all SAEs within 24 hours of receipt. This review should encompass the event, narrative, outcome, seriousness, relatedness and expectedness.

The CI will be assisted in identifying trends and maintaining oversight of IMP safety profile through trial committees as per section 27.0.

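### Sections 15.6 and 15.7 give opposite reporting instructions for incidental hospital admissions that are not related to the pregnancy

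*Protocol*

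**What the plan says.** Section 15.6 of the Protocol defines a class of "expected serious adverse events (SAEs) and will not be reported in an expedited manner". These events are still recorded. The list opens with "Events requiring hospital admission (overnight stay) which are related to the underlying pregnancy, these include" and runs through obstetric, postnatal and infant events. It closes with a different kind of item: "incidental hospital admissions for minor, gastrointestinal diseases, respiratory, cardiac, renal skin, psychiatric and neurological problems".

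Section 15.7 starts its own list with "The following will be considered Serious Adverse Events (SAEs) which will require reporting". Besides fetal, infant and maternal deaths, that list contains "Other events requiring hospital admission (overnight stay) apart from those related to the underlying pregnancy or a pregnancy related condition". The next paragraph sets the clock: "All Serious Adverse Event (SAEs) will be reported to Barts CTU, acting on behalf of the sponsor, within 24 hours". Serious adverse reactions (SARs) have their own 24-hour duty in the same paragraph.

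Four other places bear on the point:

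- Section 15.1 counts any inpatient hospitalisation as serious. Its note on exempt events describes them as related to the underlying pregnancy and refers the reader to 17.6, which is the secondary outcome analysis.
- Section 15.2 has the investigator at the coordinating centre assess causality for every SAE and expectedness for every SAR.
- Section 15.3 says that section 4.8 of the patch SmPC "will be used for assessing whether an adverse reaction is expected".
- Section 15.8 delegates the sponsor's medical assessment to the chief investigator, who "must review all SAEs within 24 hours of receipt", covering relatedness and expectedness among other things.

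**The concern.** Sections 15.6 and 15.7 are both mandatory, and they should divide SAEs cleanly between them. They appear to divide at pregnancy-relatedness: 15.1 describes the exemption that way, 15.6 opens that way, and 15.7 makes its exception that way. The last item of 15.6 crosses the line by adding admissions that are incidental to the pregnancy.

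The person completing the SAE form for such an admission therefore cannot comply with both sections. The pointer in 15.1 does not help, because it leads to a section on outcome analysis.

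The stake is safety oversight, not the efficacy result. The body systems named include the respiratory and cardiac systems, in a trial that gives one arm an inhaled nicotine product. Section 8.2 itself discusses cough and one reported lung event in e-cigarette users, and promises close monitoring of adverse events. Under 15.1 an event counts as an adverse reaction if either the reporting clinician or the sponsor suspects a causal link. That second opinion is the chief investigator's review, and its timing runs from receipt of the report. If no expedited report is sent, nothing in the protocol says when that review happens.

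**Working it through.** No figure is involved, so the check is a side-by-side reading with a test case.

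**Test case.** A participant has an overnight admission for a respiratory problem that is not related to her pregnancy.

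| Section | Does it reach this event? | Instruction |
|---|---|---|
| 15.1 | Yes: inpatient hospitalisation is an SAE. The exemption note covers pregnancy-related events only. | Not exempt |
| 15.6 | Yes: an incidental admission in a listed body system (subject to the reach of *minor*) | Record, no expedited report |
| 15.7 | Yes: an overnight admission outside the pregnancy-related exception | Report to the trials unit within 24 hours |

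The 15.6 and 15.7 rows cannot both be followed. The same result holds for each of the seven systems in the 15.6 item: gastrointestinal, respiratory, cardiac, renal, skin, psychiatric and neurological.

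**Can a reading of the text remove the conflict?**

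1. *Minor limits the exemption.* The punctuation leaves it unclear whether the word governs the whole list, only the first item, or stands as an item of its own. On the widest reach, only minor admissions are exempt. Section 15.7 has no exception for minor admissions, so a minor incidental overnight admission still falls under both rules. The conflict is smaller but remains.
2. *The incidental item belongs to the pregnancy-related heading.* An admission described as incidental is by that wording not caused by the pregnancy, so the 15.7 exception does not reach it.
3. *15.6 is a specific exception to 15.7.* Section 15.6 does refer to 15.7. But the only exception that 15.7 states for admissions is the pregnancy-related one.
4. *The all-SAE sentence is meant only for the 15.7 list.* This is the sensible reading, since otherwise 15.6 would have no effect at all. It does not help, because non-pregnancy overnight admissions are on the 15.7 list.

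**What follows for an admission handled as record-only?**

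- First assessor judges it related: it is a SAR, reportable within 24 hours under 15.7, and tested for expectedness under 15.2 and 15.3. Nothing is lost.
- First assessor judges it unrelated: it stays in the record. No expedited report goes out, so the 24-hour review in 15.8 has no stated starting point. The prompt second judgement on relatedness may not take place.

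**The case against.** The strongest reply is that the safety net is largely intact, and most of it stands. Several stronger inferences that a reader might draw are not supported.

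- **That exempted events escape causality review and so could never become SUSARs.** Section 15.2 requires causality assessment of all SAEs, whether expedited or not, and 15.7 separately requires SARs within 24 hours. Only the second review is exposed.
- **That the monitoring committee would learn of these events 6 to 12 months late because of 15.6.** Under section 27.0, SAEs that are not SUSARs go to the committee at its meetings under either rule. The meeting interval and the 24-hour clock measure different things.
- **That sites would report at different rates.** Section 15.2 places assessment at the coordinating centre, and 18.7 has the SAE forms completed there. Inconsistency between staff or over time is possible; divergence by site is not shown.
- **That 15.6 contradicts 15.3 on expectedness.** Section 15.3 governs adverse reactions, whereas 15.6 labels events without attributing cause. The two can coexist, although sharing the word *expected* invites confusion and deserves a sentence.
- **That every non-pregnancy admission in these systems is exempt.** The text says *incidental* and *minor*, and both words limit it.

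It is also fair that the events are recorded either way, so the secondary endpoint on participants with SAEs need not lose data, and the primary endpoint is untouched. The documents do not say outright which section reflects the intention. None of this tells staff which instruction to follow for a minor incidental overnight admission.

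**Conclusion.** The point holds as a contradiction between two mandatory reporting instructions, with a limited consequence. An incidental non-pregnancy admission is record-only under 15.6 and reportable within 24 hours under 15.7, and 15.1 supports the narrower exemption while citing the wrong section. The effect is possible inconsistent handling, and possible loss of the chief investigator's prompt second review for admissions that the first assessor judged unrelated.

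The size cannot be given in numbers. The protocol states no admission rates, and the class affected depends on what *minor* governs: at the least, minor incidental overnight admissions; at the most, all incidental overnight admissions in the seven systems.

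The second-review consequence rests on two assumptions. One is that the first assessor at the coordinating centre and the chief investigator (or delegate) are different people, which the protocol text at hand does not state. The other is that a record-only event is not passed to the chief investigator promptly by some other route. If either fails, the contradiction remains but costs less.

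**What to change.** 1. Reconcile 15.6 and 15.7 so that one reporting rule governs incidental non-pregnancy admissions in both arms. Which rule to keep is for the sponsor to decide; limiting 15.6 to pregnancy-related admissions would match the scope stated in 15.1 and 15.7.
2. If any exemption for incidental admissions is kept, state what *minor* governs, repair the punctuation of the list, and add the matching exception to 15.7.
3. State that the *expected* label in 15.6 does not replace the SmPC test in 15.3 for any event judged related to treatment.
4. Correct the pointer in 15.1 from 17.6 to 15.6.

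The cost is a wording amendment and, if the exemption is narrowed, possibly some additional SAE forms. No endpoint, sample size or analysis changes.
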